**Figure JJCB.5.1. Illustration of study design.**

## 5.2. Determination of Sample Size

Approximately 86 to 92 patients will be enrolled in this multicenter study.

In the Phase 1 portion of the study, the primary objective is to determine the MTD and the recommended dose for Phase 2. Approximately 13 to 16 patients will be enrolled into the adult (Part A), and approximately 13 to 16 patients will be enrolled in the pediatric (Part B) cohorts sequentially and without randomization to dose. The total sample size per cohort will be determined by DLTs.

In the Phase 2 portion of the study, the primary objective of this study is to compare the ORR (CR plus CRi) rate between LY3039478 administered with dexamethasone and placebo administered with dexamethasone, in adult patients with relapsed/refractory T-ALL/T-LBL. Approximately 60 evaluable patients will be randomized to the 2 treatment arms in a 2:1 ratio (40 randomized to LY3039478 and dexamethasone and 20 randomized to placebo and dexamethasone).

Assuming the ORR for the LY3039478 and dexamethasone arm is 40% and the ORR of the placebo and dexamethasone is 5%, the sample size of 60 evaluable patients will give approximately 82% statistical power to detect the difference, using a 2-sided Fisher's test at the significance level of 0.05, with 1 futility interim once the 30th enrolled patient completes the remission status determination.

Patients who are randomized and do not achieve a CR or CRi will be considered as nonresponders in the primary analysis for ORR.

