## 6. A Priori Statistical Methods

### 6.1. General Considerations

Phase 1 Part A, Phase 1 Part B and Phase 2 study parts will be reported in separate TFLs.

Results of descriptive analyses and estimates from inferential analyses will be presented by dose level cohort (phase 1) or by treatment (phase 2). In the phase 2 study part, an additional group will be included in primary efficacy and safety TFLs to represent data for patients receiving LY3039478 in combination with dexamethasone after failure of placebo in combination with dexamethasone.

All tests of treatment effects will be conducted at a 2-sided alpha level of 0.05, unless otherwise stated. All tests of interactions will be conducted at a 2-sided alpha level of 0.1, and all CIs will be given at a 2-sided 95% level, unless otherwise stated.

The assumptions for each statistical method will be evaluated. If there is violation of assumptions, alternative statistical methods may be used.

Additional exploratory analyses of the data will be conducted as deemed appropriate.

For continuous variables, summary statistics will include number of patients, mean, median, standard deviation, minimum, and maximum. Categorical endpoints will be summarized using number of patients, frequency, and percentages. Any missing longitudinal data will not be imputed, rather estimated from an appropriate random mixed effects model. Transformations will be applied where assumptions behind any analysis are better satisfied by data being transformed onto an alternative scale. All results from any of these analyses will be back transformed to the original scale. Alternatively, nonparametric methods will be applied.

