## 6.8. Patient Characteristics

Patient demographics including age, sex, screening height, weight and body mass index, race, ethnicity, patient habits (caffeine/alcohol use) and country will be reported using descriptive statistics.

Baseline disease characteristics will be summarized by cohort (phase 1a, phase 1b) or randomized treatment arm (phase 2). Continuous variables will be summarized by median and range, and compared amongst treatment arms by ANOVA. Categorical variables will be summarized by frequency counts and compared amongst treatment arms by Fishers exact test. Statistical comparisons will be provided in phase 2 where data warrant only. The following disease characteristics will be summarized:

- Sex
- Age
- Diagnosis: T-ALL and T-LBL, with T-ALL additionally split by subtype:

TdT+, variable for all of the following: CD1a, CD2, CD3, CD4, CD5, CD7, CD8, CD34

- Pro-T-ALL: cCD3+, CD7+, CD1a-, CD2-, CD4-, CD8-, CD34+/-
- Pre-T-ALL: cCD3+, CD7+, CD1a-, CD2+, CD4-, CD8-, CD34+/-
- Cortical T-ALL: cCD3+, CD7+, CD1a+, CD2+, CD4+, CD8+, CD34-
- Medullary T-ALL: cCD3+, sCD3+, CD7+, CD1a-, CD2+, CD4+or CD8+, CD34-
- ETP T-ALL: Lack of CD1a and CD8 expression, weak CD5 expression with less than 75% positive blasts, and expression of 1 or more of the following myeloid or stem cell markers on at least 25% of lymphoblasts: CD117, CD34, HLA-DR, CD13, CD33, CD11b, and/or CD65
- ECOG status at randomization, or Lanksky status for Phase 1 Part B (pediatrics)
- Disease status: Refractory or relapsed, with relapse additionally split by: first relapse, second relapse, relapse after SCT
- Notch and/or FBWX7 mutational status: Yes, no [See Trinquand et al, 2013 for further details]
- RAS and/or PTEN abnormalities: Yes, no [See Trinquand et al, 2013 for further details]
- Extramedullary disease: Yes, no
- History of CNS leukemia: Yes, no
- Time since initial diagnosis
- Duration of first remission
- Response to last therapy: refractory, or relapsed with duration of remission <1 year, 1-2 years, 2-5 years, >5 years
- Number of prior courses of induction therapy (1, 2, 3, ≥4)
- Country

Other patient characteristics will be summarized as deemed appropriate.

Prior therapies and procedures e.g. stem cell transplant will be listed.

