#### **Time to Event Endpoints**

For the secondary efficacy endpoints OS, RFS, and EFS, the Kaplan-Meier method (Kaplan and Meier 1958) will be used to estimate the survival curves as well as survival rates at various

prespecified time points (12 months for OS, 6 and 12 months for RFS and EFS) for each treatment arm.

The secondary efficacy endpoint DoR is subject to competing risk of death without relapse; therefore, the cumulative incidence of relapse (Gray 1988; Pepe and Mori 1993; Gooley et al. 2001) will be used. In the calculation, patients who did not have the event will be considered right-censored observations.

The comparison of the survival curves between treatment groups will be conducted by a log-rank test. Exploratory analyses for the comparison of the survival curves between treatment groups may additionally be conducted by a stratified log-rank test with some of the following stratification variables: initial diagnosis (T-ALL phenotype, T-LBL), response to last therapy (refractory or relapsed), age, number of prior therapies ( $\leq 2$ ,  $> 2$ ), NOTCH-1/FBXW7/RAS/PTEN status.

The Cox proportional hazard model (Cox 1972) with treatment as a factor will be used to estimate the hazard ratio and corresponding 95% CI with Wald's test p-value after adjusting for the following potential predictive/prognostic variables: initial diagnosis (T-ALL phenotype, T-LBL), response to last therapy (refractory or relapsed), age, number of prior therapies ( $\leq 2$ ,  $> 2$ ), NOTCH-1/FBXW7/RAS/PTEN status.

The unadjusted impact of patient baseline disease characteristics listed in Section 6.8 on OS and EFS will be explored using Cox proportional hazard models (Cox 1972) with the baseline characteristic as a factor (continuous variables split at median) and the hazard ratio and corresponding 95% CI plotted on a forest plot. Any characteristics found to be significant prognostic markers for EFS or OR may be included as additional covariates in COX proportional hazard model analyses to compare treatment arms.

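### Splitting continuous baseline characteristics at the median in the exploratory OS and EFS Cox models gives up power that a continuous term would keep when the effect is roughly log-linear

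*SAP*

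**What the plan says.** SAP 6.11.3, under the time-to-event endpoints: "The unadjusted impact of patient baseline disease characteristics listed in Section 6.8 on OS and EFS will be explored using Cox proportional hazard models", "with the baseline characteristic as a factor (continuous variables split at median". The hazard ratios and 95% confidence intervals go on a forest plot. Most items in SAP 6.8 are categorical. The continuous ones are age, duration of first remission and "Time since initial diagnosis".

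The next sentence allows the results to be used further: "Any characteristics found to be significant prognostic markers for EFS or OR may be included as additional covariates in COX proportional hazard model analyses". (The screen is run on OS and EFS, so the second endpoint named there is presumably OS.) Inclusion is optional, and the SAP does not say whether a covariate would enter split or continuous.

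The same section separately pre-specifies an adjusted Cox model for the treatment effect. It contains initial diagnosis, "response to last therapy (refractory or relapsed), age, number of prior therapies" and mutation status, whatever the screen shows. The form of age in that model is not stated.

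Neither document gives a reason for the split, or an event count, effect size or power for the prognostic models.

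**The concern.** A median split treats a patient just above the median like one at the extreme, and a patient just below it like one far below. When risk changes smoothly with the covariate, this discards information, and a trial of 60 patients has little to spare. A real prognostic factor is then more likely to be missed.

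The SAP does not say which median it means. If it is the median of the trial data, the cut is unknown until the data are in and the hazard ratio is tied to it. For age, it need not coincide with the 30-year cut used for allocation (SAP 5.3.2) and for subgroups (Protocol 12.2.13), so age could be reported on two different splits.

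If a split covariate is later used to adjust the treatment comparison, it removes less prognostic variation than its continuous form would.

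**Working it through.** **The plan's own figure.** The only stated power, about 82%, is for the ORR comparison with "40 randomized to LY3039478 and dexamethasone and 20 randomized to placebo and dexamethasone". The Walters arcsine approximation for Fisher's test gives 82.2%, so the figure reproduces, but it says nothing about the prognostic models.

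**Inputs.** From the documents: 60 Phase 2 patients (SAP 5.2) and a two-sided 0.05 level (SAP 6.1, stated there for treatment effects and used here for the screen too). Assumed: 51 events (85%), hazard ratio (HR) 1.3 to 1.7 per standard deviation (SD), log-linear effect, normal covariate.

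**Step 1, information kept.** For a normal covariate a median split keeps 2/π = 0.637 of the information, so 1 − 0.637 = 36% is lost.

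**Step 2, events needed.** Events for 80% power = (1.96 + 0.842)² / (ln HR)². At HR 1.5 per SD this is 7.85 / 0.1644 ≈ 48 with a continuous term. With the split it is 48 × π/2 ≈ 75, more than the 60 patients could supply.

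**Step 3, power by approximation.** Power = Φ(√d × ln HR × √e − 1.96), with d = 51 events and e = 1 (continuous) or 0.637 (split). At HR 1.5:
- continuous: Φ(7.14 × 0.405 − 1.96) = Φ(0.94) ≈ 83%
- split: Φ(7.14 × 0.405 × 0.798 − 1.96) = Φ(0.35) ≈ 64%

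**Step 4, power by simulation.** Single-covariate Cox models, Wald test, 60 patients and 51 events, normal covariate. Repeat runs agree to about 2 points.

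| HR per SD | Continuous | Median split | Loss (points) |
|---|---|---|---|
| 1.3 | 44% | 30% | 14 |
| 1.5 | 78% | 56% | 22 |
| 1.7 | 94% | 79% | 15 |

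At HR 1.0 both forms reject about 5% of the time.

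**Step 5, sensitivity to the assumptions.** Over 30 to 60 events and HR 1.25 to 2.5 per SD, the loss is:
- 0.4 to 22 points for a normal covariate, smallest where the effect is strongest
- 0.1 to 15 points for a uniform covariate
- 21 to 51 points for a lognormal covariate whose effect is linear on the raw scale and fitted on that scale

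**Step 6, a true step instead of a slope.** Step of HR 2, normal covariate, about 85% events:

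| Step at percentile | Continuous | Median split |
|---|---|---|
| 40th | 46% | 50% |
| 45th | 47% | 55% |
| 50th | 49% | 58% |
| 55th | 47% | 54% |
| 60th | 43% | 44% |

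**Step 7, later adjustment.** 60 patients at 40:20, 45 events, treatment HR 0.5. Power for the treatment effect:

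| Covariate HR per SD | Unadjusted | Split-adjusted | Continuous-adjusted |
|---|---|---|---|
| 1.5 | 51% | 55% | 57% |
| 2.0 | 41% | 51% | 57% |

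The split costs 57 − 55 = 2 and 57 − 51 = 6 points against the continuous form, and still beats no adjustment. Type I error was 4.6% to 5.7% throughout.

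**The case against.** The strongest reply is that little hangs on this. The models are unadjusted and exploratory, touch about three characteristics and feed no decision rule. SAP 6.1 already allows transformations, alternative methods and further exploratory analyses. This stands, and it limits the point to a minor improvement.

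The size is also not a document figure, since events, effect and distribution are all assumed. For duration of first remission even 60 patients may be too many: Protocol 7.1 admits initially refractory patients, who may have had no first remission. This stands too.

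A reader might infer larger losses, up to about 38 points, for a skewed covariate such as time since diagnosis. They arise only if the effect is linear on the raw skewed scale and the model is fitted on that scale. With an exponential covariate of that kind at HR 1.3, 1.5 and 1.7, power was 44%, 78% and 92% for a raw term, 24%, 46% and 64% for a log term, and 22%, 40% and 57% for the split. A log term chosen only because the covariate is skewed would gain just 2 to 7 points there, or up to about 9 in a repeat run. The scale therefore has to be chosen on clinical grounds.

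A reader might also infer that the split wins only if the step lies exactly at the median, or that it weakens every later adjustment. Step 6 contradicts the first. On the second, the SAP says only that significant characteristics "may be included as additional covariates in COX proportional hazard model analyses to compare treatment arms", without giving their form, and the five-variable model stands apart from the screen. For age, allocation is already balanced at 30 years.

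None of this is a reason to keep the split as the scale of analysis.

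**Conclusion.** The point holds as a minor one. SAP 6.11.3 prescribes a median split without giving a reason. Under a roughly log-linear effect of a normal covariate it discards about 36% of the information, which is about 14 to 22 points of power at 51 assumed events and HR 1.3 to 1.7 per SD. The documents support no single figure beyond that illustration: the loss shrinks to near zero for very strong effects, and the split ties or wins for a step between about the 40th and 60th percentiles.

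The effect on a treatment comparison is conditional. It arises only if a screened covariate is added and enters in split form, and it is then about 2 to 6 points under the assumptions of step 7. The documents do not support reading this as a flaw in the primary ORR test, the log-rank tests or the pre-specified Cox model.

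**What to change.** In SAP 6.11.3, replace the parenthesis on the median split with wording to this effect:
- Continuous characteristics enter the Cox models as continuous terms, on a raw or log scale fixed in advance for each on clinical grounds, not by skewness alone.
- The forest plot shows the hazard ratio and 95% CI per a stated fixed unit, for example per 10 years of age. A fixed unit is preferable to a sample SD or interquartile range, which also vary with the data.
- A characteristic carried into a treatment model keeps the same form.
- Median or 30-year splits are for display only.

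The cost is one line of SAP text and a label on the forest plot, with no extra data, patients or procedures. The downside is the assumption of a roughly linear log-hazard, which can be checked.

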#### **6.11.4. Sensitivity Analyses**

For the analysis of time-to-event endpoints EFS and RFS, sensitivity analysis definitions as described in table JJCB.6.2 will be completed for the log-rank test. Such analyses will only be conducted if the primary analysis of such endpoints warrants sensitivity analysis to evaluate whether and to what extent the conclusion would be affected under the different censoring rules.

For the analysis of OS, sensitivity analysis definition SA1 as described in Table JJCB.6.2 will also be completed. Further analyses may explore OS adjusting for patients which received LY3039478 plus dexamethasone following treatment failure of placebo plus dexamethasone, if warranted.

Additionally, analyses may be conducted (if applicable) excluding patients that are randomized but do not receive treatment, and by actual treatment received.

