12.2. Statistical and Analytical Plans

12.2.1. General Considerations

Statistical analysis of this study will be the responsibility of Lilly.

Efficacy analyses will be based on the intention-to-treat (ITT) analysis set. This population is defined as all patients randomized to study treatment. Patients will be grouped according to dose level cohort or randomized treatment. Sensitivity analyses may be conducted (if applicable) excluding patients that are randomized but do not receive treatment, and by actual treatment received.

A secondary analysis of the primary efficacy endpoint based upon the per-protocol set (PPS) of patients may be performed if there are significant numbers of patients with major protocol deviations ($\geq 10\%$ of total patient population). The PPS is defined as those patients in the ITT set who are compliant with the study protocol. Major deviations from the protocol for purposes of this analysis will be detailed in the Statistical Analysis Plan.

Safety analyses will be based on the safety population, defined as all enrolled patients receiving at least 1 dose of any study drug. Patients will be grouped according to treatment received in Cycle 1.

PD and/or tailoring biomarker analyses will be based on the subset of patients from the above populations from whom a valid assay result (according to laboratory guideline) has been obtained.

All tests of treatment effects will be conducted at a 2-sided alpha level of 0.05, unless otherwise stated. All tests of interactions will be conducted at a 2-sided alpha level of 0.1, and all CIs will be given at a 2-sided 95% level, unless otherwise stated.

Any change to the data analysis methods described in the protocol will require an amendment ONLY if it changes a principal feature of the protocol.

Before unblinding of the aggregate database, minor modifications or clarifications to the data analysis methods may be described and justified in the statistical analysis plan.

Any other change to the data analysis methods described in the protocol, and the justification for making the change, will be described in the clinical study report.

The assumptions for each statistical method will be evaluated. If there is violation of assumptions, alternative statistical methods may be used.

Additional exploratory analyses of the data will be conducted as deemed appropriate.

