12.2.8. Other Analyses of Efficacy

No formal efficacy analysis is planned for the Phase 1 portion of this trial. However, any response data will be listed and tabulated.

In Phase 2, the following secondary efficacy parameters will be summarized for each treatment arm:

- Proportion of patients achieving a ORR or PR
- Proportion of patients achieving a CR, CRi, and PR
- OS
- RFS
- EFS
- DoR

The secondary efficacy endpoints of proportion of patients achieving ORR plus PR, and PR, and their exact 95% CIs will be estimated for each treatment arm and compared by 2-sided Chi-squared test or Fisher's exact test between 2 arms. A Fisher's exact test will be chosen over

a Chi-squared test if in the 2x2 table, any of the expected cell counts are less than 5, or any cell has zero counts.

For the secondary efficacy endpoints OS, RFS, and EFS, the Kaplan-Meier method (Kaplan and Meier 1958) will be used to estimate the survival curves as well as survival rates at various prespecified time points (12 months for OS, 6 and 12 months for RFS and EFS) for each treatment arm.

The secondary efficacy endpoint DoR is subject to competing risk of death without relapse; therefore, the cumulative incidence of relapse (Gray 1988; Pepe and Mori 1993; Gooley et al. 2001) will be used. In the calculation, patients who did not have the event will be considered right-censored observations. All randomized patients, according to the ITT principle, will be included in the analysis of these endpoints.

The comparison of the survival curves between treatment groups will be conducted by a log-rank test. Exploratory analyses for the comparison of the survival curves between treatment groups may be conducted by a stratified log-rank test with some of the following stratification variables: initial diagnosis (T-ALL phenotype, T-LBL), response to last therapy (refractory or relapsed), age, number of prior therapies (≤ 2 , > 2), NOTCH-1/FBXW7/RAS/PTEN status.

The Cox proportional hazard model (Cox 1972) with treatment as a factor will be used to estimate the hazard ratio and corresponding 95% CI with Wald's test p-value after adjusting for the following potential predictive/prognostic variables: initial diagnosis (T-ALL phenotype, T-LBL), response to last therapy (refractory or relapsed), age, number of prior therapies (≤ 2 , > 2), NOTCH-1/FBXW7/RAS/PTEN status.

All randomized patients, according to the ITT principle, will be included in the analysis of these endpoints.

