For the analysis of time-to-event endpoints, a sensitivity analysis censoring the event time at the date of SCT will be completed to evaluate the potential impact from imbalance in patients receiving transplantation between the study arms.

No missing data will be imputed.

Efficacy data (CR, CRi, PR, and ORR) for patients receiving patients receiving LY3039478 in combination with dexamethasone after failure of placebo in combination with dexamethasone will be tabulated, and further exploratory analyses of efficacy data conducted as warranted.

Additional exploratory analyses may be performed as deemed appropriate.

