**Table JJCB.6.2. Censoring Rules Sensitivity Analysis Definitions**

Sensitivity Analysis Definition #	Situation	Date of Progression or Censor	Censored / Progressed
SA 1	Patient receives stem cell transplant before relapse, progression or death	Date of stem cell transplant	Censored
SA 2	Relapsed disease, progressive disease or death after $\geq 2$ missed assessments, including blood/bone marrow samples, CT/MRI or PET assessments.	Date of last post baseline assessment before missed assessments or Date of randomization (for EFS) or disease-free state (for RFS) if no other assessment in between	Censored
SA 3	Patient does not have adequate baseline assessment (bone marrow biopsy/aspirate or PET-CT, or CT-MRI)	Date of randomization for EFS analysis Patient not eligible for RFS analysis	Censored
SA 4	Patient is lost to follow-up without relapsed or progressive disease	Date of next scheduled post baseline adequate assessment at or after becoming lost to follow-up	Progressed
SA 5	Patient is lost to follow-up without relapsed or progressive disease	Date of next scheduled post baseline adequate assessment at or after becoming lost to follow-up	Progressed for the treatment arm and censored for the control arm

- Duration of Response (DoR)** DoR for T-ALL is measured from the date of CR, CRi or PR by blood count recovery and bone marrow examination, until the date of relapse. DoR for T-LBL is measured from the time when criteria for response (ie, CR or PR) are met, until the first documentation of relapse or progression. For patients who die without report of relapse, DoR is censored on the date of death, regardless of cause. For a patient with no report of relapse or death by the end of the follow-up data collection, observation is censored at the date of last contact prior to the data inclusion cutoff date.

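### SAP 6.11.4 makes the transplant-censored analysis of EFS and RFS depend on the observed result, although the protocol commits to it without condition

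*SAP*

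**What the plan says.** Protocol 12.2.8 lists the endpoints: "For the secondary efficacy endpoints OS, RFS, and EFS, the Kaplan-Meier method (Kaplan and Meier 1958) will be used to estimate the survival curves". DoR is handled separately, by cumulative incidence of relapse. For time-to-event endpoints the same section then promises a transplant check: "a sensitivity analysis censoring the event time at the date of SCT will be completed to evaluate the potential impact from imbalance". The imbalance meant is a difference between the arms in who receives a transplant. The sentence carries no condition.

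SAP Table JJCB.6.2 turns this into rule SA1. It applies where "Patient receives stem cell transplant before relapse, progression or death", and the patient is censored at the transplant date. The table adds four other rules: SA2 (event after two or more missed assessments), SA3 (no adequate baseline assessment), and SA4 and SA5 (loss to follow-up, counted as progression in both arms or in the treatment arm only).

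SAP 6.11.4 says when the rules are used. For two endpoints it begins: "For the analysis of time-to-event endpoints EFS and RFS, sensitivity analysis definitions as described in table JJCB.6.2 will be completed for the log-rank test". The next sentence reads: "Such analyses will only be conducted if the primary analysis of such endpoints warrants sensitivity analysis". It goes on to give the aim, which is to see whether other censoring rules would change the conclusion. A separate paragraph deals with survival: "For the analysis of OS, sensitivity analysis definition SA1 as described in Table JJCB.6.2 will also be completed".

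**The concern.** A sensitivity analysis is persuasive when it is reported however the main analysis turns out. If someone may decide, after seeing the comparison of the arms, whether the check is needed, a reader of the study report cannot tell whether a missing check was unnecessary or unwelcome.

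The trigger also does not fit the purpose. The protocol wants the analysis because transplantation may be unequal between arms. That inequality can exist whether the EFS or RFS comparison looks positive or null. A trigger tied to the endpoint result could therefore leave the analysis out in just the situation it was meant for.

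**Working it through.** There is no planned figure to reproduce, since the point rests on no sample size, power or event count. The check is a comparison of texts.

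**Step 1. Status of transplant censoring, endpoint by endpoint.**

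| Endpoint | Protocol 12.2.8 | SAP 6.11.4 | Agreement |
|---|---|---|---|
| OS | Committed, no condition | SA1 committed, no condition | Yes |
| EFS | Committed, no condition | SA1 only if the main analysis warrants it | No |
| RFS | Committed, no condition | SA1 only if the main analysis warrants it | No |

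The conditional sentence follows directly on the one naming EFS and RFS and refers back to it. The OS sentence stands in its own paragraph and does not repeat the condition. The conflict is therefore confined to EFS and RFS.

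**Step 2. Consistency within the SAP.** For EFS and RFS, one sentence says the Table JJCB.6.2 analyses will be completed, and the next says they will be done only in some circumstances. A programmer could follow either.

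**Step 3. The trigger.** What has to warrant the analyses is the main analysis of the endpoint itself. No p-value, event count, number of transplants or number of missed assessments is given. The decision would thus be made after the arms have been compared, and with no rule.

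**Step 4. Is the departure authorised?** Protocol 12.2.1 provides that, before unblinding, "minor modifications or clarifications to the data analysis methods may be described and justified in the statistical analysis plan". The SAP text describes the condition but offers no justification for it. Nor does it explain why the same analysis is firm for OS and optional for EFS and RFS.

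**Step 5. Size.** The effect of SA1 on an EFS or RFS comparison depends on how many patients in each arm are transplanted before an event, and when. Neither document states or assumes a transplant rate, so no magnitude can be calculated.

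**The case against.** The best defence is that the methods are not chosen after the fact. Each rule is written out in Table JJCB.6.2, and the SAP revision history records approval of Version 1 before the first visit at which a subject receives study drug. Only the decision to run the rules is left open, and its stated aim is legitimate. This stands, and it limits the criticism to an undefined, result-dependent trigger. A charitable reader might add that the condition merely avoids empty tables, since SA1 reproduces the main analysis if nobody is transplanted. The SAP does not say that, however. It ties the decision to the endpoint analysis and not to the number of patients a rule affects.

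It is also fair to say that little hangs on this. EFS and RFS are secondary, and SAP 6.5 plans no multiplicity adjustment. Under the sample-size assumptions, about 0.05 × 20 = 1 control patient would respond. The between-arm RFS comparison would then be nearly uninformative with or without SA1.

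Four stronger readings are tempting, and the documents do not support them:

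- *The SAP drops transplant censoring for all time-to-event endpoints.* It keeps SA1 for OS.
- *Making SA2 to SA5 conditional breaks the protocol.* The protocol sentence covers transplant censoring only, and the other four rules are SAP additions.
- *Checks run under this clause cannot show robustness.* The rules are fixed in advance. What suffers is the assurance that they are reported whatever the result.
- *Transplant rates could differ by up to 35 percentage points.* A reader might get this from the assumed ORRs: 0.40 × 40 = 16 responders against 0.05 × 20 = 1, or 40% − 5% = 35 points. That is a response difference. Reading it as a transplant difference assumes that every responder and no non-responder is transplanted. Neither document links transplant to response (Protocol 12.2.5 lists it only as a post-discontinuation therapy), and crossover responders could narrow the gap. It is not a true upper bound, and it does not measure bias in EFS or RFS.

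**Conclusion.** The conflict is real and narrow. Transplant censoring of EFS and RFS is promised unconditionally in the protocol. The SAP makes it depend on the observed result, with no criterion and no justification, and contradicts its own preceding sentence. Followed as written, SAP 6.11.4 would allow the transplant-imbalance check to be omitted for these two endpoints.

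The finding is minor. It affects two secondary endpoints and leaves the primary ORR analysis and the OS analysis as they are. No numerical size can be attached. The conclusion rests only on reading the protocol's reference to time-to-event endpoints as including EFS and RFS, which the same section analyses with Kaplan-Meier curves and log-rank tests. It does not assume that transplantation will in fact be unequal.

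**What to change.** Before unblinding, delete the conditional sentence in SAP 6.11.4. State in its place that SA1 will be carried out for both EFS and RFS regardless of the main result, as Protocol 12.2.8 requires. The OS sentence needs no change.

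Preferably, say the same for SA2 to SA5. This is a recommendation, not a matter of protocol compliance. SA5 shows why it helps: it counts loss to follow-up as progression in the treatment arm but as censoring in the control arm, so it is deliberately unfavourable to the test treatment and most credible when always reported. If the sponsor wants to keep a trigger for these four, it should be objective, fixed before unblinding and independent of the treatment comparison. The number of patients with missed assessments or lost to follow-up would serve.

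The cost is an edit to one paragraph and a few extra tables from definitions that already exist. No additional data or patients are needed.
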